10. ANALYSIS POPULATIONS

10.1. Intent-to-Treatment Population

The Intent-to-Treat (ITT) population is defined as all subjects randomized and received treatment after randomization. The ITT population will be used for the analysis of exploratory and safety endpoints.

10.2. Per Protocol Population

The Per Protocol (PP) population is defined as all randomized subjects who were not associated with a major protocol violation. This population will be identified before the database lock. The PP analysis of primary and secondary endpoints will be considered supportive.

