10.4. Primary Efficacy Population

Due to COVID-19 restrictions on clinical trial operation at many sites, and the reality that the study did not experience the anticipated 15% “Lost to Follow Up” figures assumed, a decision was made to terminate screening/enrollment prior to reaching the full enrollment of 240. As a result, 5/21/2020 was determined as the date for determining the primary analysis set. To accommodate for the schedule of events within the protocol, it was determined that subjects randomized by 3/3/2020 will be included in the PEP. All randomized subjects within the PEP will have enough time to go through the 12 weeks treatment phase by 5/21/2020.

The PEP will be used for the analysis of primary and secondary endpoints.

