11.1.1 Timing of Primary Analysis

The primary efficacy analysis will be conducted when all patients who were randomized on or before 03 March 2020 completes up to 12 weeks of treatment and follow up (see primary efficacy population of Section 10.4). Based on this enrollment cut-off date, 207 patients will be included in the PEP.

The safety analysis will be performed on safety population. . The results will be generated based on final database lock.

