11.4. Prognostic Factors Assessments

For the ITT population, a covariate analysis will be conducted to assess the impact of various prognostic factors on ulcer closure and to demonstrate the robustness of the primary efficacy analysis. Prognostic factors (i.e., covariates) will be included if they are found to be contributing factors (i.e., the individual covariate p-value is less than 0.05). Potential prognostic factors to be considered include:

Baseline ulcer size	Diabetes type
Age of ulcer at baseline	Race
Gender	Nicotine Use
Recorded HbA1c	Baseline BMI
Ulcer volume	Ulcer location

Additional planned analyses include the use of Analysis of Covariance (ANCOVA) models which incorporate consideration of stratification factors (i.e., site and baseline ulcer area) to compare reduction in study ulcer size between the two treatment groups and Kaplan-Meier analysis to assess and describe the differences in the time to wound closure in the two treatment groups.

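### The two analyses labelled as robustness checks of the primary result (PP, and covariates in ITT) are not confined to the primary set, so agreement or disagreement with it cannot be put down to one cause

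*SAP*

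**What the plan says.** **Primary set.** SAP 10.4 defines the PEP by date of randomisation: "it was determined that subjects randomized by 3/3/2020 will be included in the PEP". It assigns the primary and secondary endpoints to this set. SAP 11.1.1 gives its size: "Based on this enrollment cut-off date, 207 patients will be included in the PEP".

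**First check.** SAP 12.8 plans a supportive PP analysis to assess robustness of the primary result, using the same method in a different population. SAP 11 calls it the sensitivity analysis of the primary endpoint. Its population is set in SAP 10.2: "The Per Protocol (PP) population is defined as all randomized subjects who were not associated with a major protocol violation".

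**Second check.** SAP 11.4 states: "For the ITT population, a covariate analysis will be conducted to assess the impact of various prognostic factors on ulcer closure". It gives a second purpose, to show that the primary efficacy analysis is robust. SAP 10.1 defines the set: "The Intent-to-Treat (ITT) population is defined as all subjects randomized and received treatment after randomization". The same section reserves ITT for exploratory and safety endpoints.

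**Protocol sets.** In protocol 8.10.1 the primary set was all randomised subjects. PP (8.10.2) was a subset of it, and the covariate analysis (8.12.1) used that same primary set.

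**The concern.** A robustness check is most informative when it changes one thing and leaves the rest alone. Under the protocol both checks did so: PP removed violators from the primary set, and the covariate analysis changed the model within it. The SAP changed the primary set to the PEP but left the populations of the two checks undated, and nothing elsewhere in the SAP restricts them to PEP members.

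Both checks now make two changes at once. PP takes violators out and brings subjects randomised after 3 March 2020 in. The covariate analysis adjusts the model and also moves to a different set of subjects. If either departs from the primary result, the planned outputs do not show which change was responsible. Agreement is no clearer, because the two changes could offset each other. The primary test itself is not affected; at stake is what the two supporting analyses can say about it.

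**Working it through.** **1. Set logic.**

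| Set | Where | Date limit | Other condition |
|---|---|---|---|
| PEP | SAP 10.4 | randomised by 3 March 2020 | none stated |
| PP | SAP 10.2 | none | no major protocol violation |
| ITT | SAP 10.1 | none | treated after randomisation |

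A subject randomised after 3 March 2020, treated and without a major violation is in PP and ITT but not in the PEP. So neither PP nor ITT is a subset of the PEP by definition. Conversely, a subject randomised before the cut-off but never treated is in the PEP as worded and not in ITT, so PEP and ITT are nested in neither direction.

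**2. The plan's own figure.** SAP 6 needs 204 subjects and expects 15% discontinuation: 204 / (1 − 0.15) = 240. This is the SAP's planned number randomised, and it reproduces.

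**3. Bound on late subjects.** SAP 10.4 says "a decision was made to terminate screening/enrollment prior to reaching the full enrollment of 240". Total randomised is therefore at most 239. With 207 in the PEP, late subjects number between 0 and 239 − 207 = 32. The largest share is 32 / 239 = 13.4%.

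**4. Effect on the estimate.** With L late subjects split 1:1, difference d among them, a 20-point PEP difference (the planned 46% against 26%) and no PP exclusions:

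pooled difference = (207 × 20 + L × d) / (207 + L)

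| L | d (points) | Pooled difference (points) |
|---|---|---|
| 5 | 0 | 4140 / 212 = 19.5 |
| 32 | 0 | 4140 / 239 = 17.3 |
| 32 | −20 | 3500 / 239 = 14.6 |
| 32 | +20 | 4780 / 239 = 20.0 |

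These shifts arise with no violator removed and no covariate added.

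**5. Effect on a p-value.** This uses an unstratified z-test, mean closure 36% (midway between 46% and 26%) and equal arms. Take a PEP difference of 15 points.

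- PEP, 103.5 per arm: SE = √(0.36 × 0.64 × 2 / 103.5) = 0.0667; z = 0.15 / 0.0667 = 2.25; p = 0.025.
- With 32 late subjects showing no difference, 119.5 per arm: pooled difference = 207 × 15 / 239 = 13.0 points; SE = √(0.36 × 0.64 × 2 / 119.5) = 0.0621; z = 2.09; p = 0.036.

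The first is below the final two-sided level of 0.028 in SAP 6 and the second is above it, from the late subjects alone. This is an extreme case within the bound, chosen to show that the effect need not be negligible.

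**The case against.** **The sets are the protocol's own.** PP from all randomised subjects and covariates in ITT were prespecified. The SAP's covariate analysis is also the planned closure analysis that uses all randomised and treated subjects, which partly offsets the move away from an ITT primary set. Replacing it outright could leave no unrestricted analysis. This stands, and the fix therefore adds PEP versions and keeps an all-randomised one.

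**It may be a deliberate test of the cut-off.** No section says so. It would be a poor test, because PP removes violators and the covariate analysis changes the model at the same time.

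**The number may be trivial.** It may be 0 or a handful, and with 5 late subjects the illustrated shift is half a point. This stands. A reader might take 256 from the protocol and reach 49 late subjects, but SAP 10.4 caps the total below 240.

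**Stronger readings that the documents do not support.**

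- A reader might infer that every check of the primary endpoint is affected. The site 109 sensitivity analysis (SAP 13.1) runs in the primary set.
- A reader might infer that a disagreement is uninterpretable. It cannot be attributed to one cause from the planned outputs, but the late group is bounded and identified by date, so extra analyses can separate its contribution.
- A reader might infer that only late subjects were exposed to COVID-19 restrictions. SAP 10.4 does not date them, and PEP subjects were followed towards 21 May 2020.
- A reader might infer that PP membership will be chosen after the primary result is known. SAP 10.2 fixes PP before database lock. The sentence in 11.1.1, "The results will be generated based on final database lock", follows directly on the safety analysis and its scope is unclear. Protocol 10.1 places the final analysis after data verification and describes one final lock. Late selection of PP in this open-label trial is a possibility that the text leaves open, not something it shows.

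**Conclusion.** The point holds by the written definitions: neither of the two analyses that the SAP labels as robustness checks is confined to the PEP. Each mixes its intended change with a change of subjects, so its result cannot be attributed to one cause. Most likely the two definitions were carried over when the primary set was changed.

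The size is limited and unknown: 0 to 32 late subjects, at most 13.4% of all randomised. The 17.3-point figure assumes the maximum number, a 1:1 split, no effect in late subjects and no PP exclusions; the documents give no evidence on the effect in late subjects. The primary test and its decision rule are untouched, and the PP analysis is only supportive. The SAP should be changed because the correction is cheap and lets both checks do their stated job.

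**What to change.** - In SAP 10.2 and 12.8, run the supportive PP analysis in PEP subjects without a major protocol violation.
- In SAP 11.4, run the covariate analysis in the PEP.
- Keep the primary CMH test in all randomised subjects, and the covariate model there if wanted, as a separate, labelled sensitivity analysis of the cut-off.
- Report the number randomised after 3 March 2020, by arm.
- State in 10.2 that the PP list is fixed before the primary efficacy analysis is run, and clarify in 11.1.1 whether the final-lock sentence covers efficacy or safety only.

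The cost is SAP wording and a few extra outputs. The PP set loses any late subjects, who remain in the all-randomised analysis. The site 109 analysis needs no change.

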10.3. Safety Population

The Safety Population is defined the same as ITT. This population will be used for the analysis of safety parameters.

10.4. Primary Efficacy Population

Due to COVID-19 restrictions on clinical trial operation at many sites, and the reality that the study did not experience the anticipated 15% “Lost to Follow Up” figures assumed, a decision was made to terminate screening/enrollment prior to reaching the full enrollment of 240. As a result, 5/21/2020 was determined as the date for determining the primary analysis set. To accommodate for the schedule of events within the protocol, it was determined that subjects randomized by 3/3/2020 will be included in the PEP. All randomized subjects within the PEP will have enough time to go through the 12 weeks treatment phase by 5/21/2020.

The PEP will be used for the analysis of primary and secondary endpoints.

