5.1. Study Flow Chart

5.2. Schedule of Events

Procedure	Screening Phase		Treatment Phase													Follow-Up Phase	
	SV 1 -14±3d	SV 2 -7±3d	Randomization/ TV ³ 1 (Day 0)	TV 2 7±3d	TV 3 14±3d	TV 4 21±3d	TV 5 28±3d	TV 6 35±3d	TV 7 42±3d	TV 8 49±3d	TV 9 56±3d	TV 10 63±3d	TV 11 70±3d	TV 12 77±3d	TV 13 84±3d	Conf Visit 7±3d After Closure	4-Week 28±3d After Confirm.
Inf. Consent/HIPAA	X																
Inclusion/Exclusion	X	X	X														
MRU Assessment	X	X	X	X	X	X	X	X	X	X	X	X	X	X	X	X	
Demographics	X																
Medical History	X																
Physical Exam	X																
Vascular Perfusion	X																
Ulcer Assessments ⁴	X	X	X	X	X	X	X	X	X	X	X	X	X	X	X	X	
Ulcer Photography	X ⁵	X ⁶	X ^{6,7}	X ⁶	X ⁸												
Ulcer Debridement	X	X ⁹	X	X ⁹													
Ulcer Measurement	X	X	X	X	X	X	X	X	X	X	X	X	X	X	X		
Control Treatment	X	X	X ¹⁰	X ¹⁰	X ¹⁰	X ¹⁰	X ¹⁰	X ¹⁰	X ¹⁰	X ¹⁰	X ¹⁰	X ¹⁰	X ¹⁰	X ¹⁰	X ¹⁰		
Treatment Compliance	X	X	X	X	X	X	X	X	X	X	X	X	X	X	X		
Offloading ¹¹	X	X	X	X	X	X	X	X	X	X	X	X	X	X	X		
Concomitant Meds	X	X	X	X	X	X	X	X	X	X	X	X	X	X	X		
Adverse Events		X	X	X	X	X	X	X	X	X	X	X	X	X	X	X	
Ulcer Size Reduction			X														
Randomization			X														
Active Treatment			X ¹²	X ¹³													
Closure Assessment			X	X	X	X	X	X	X	X	X	X	X	X	X ¹⁴	X	

¹ Only to be used for a visit that falls out of range of one of the other visit windows. If the proposed Unscheduled Visit falls within the next visit window, use that visit instead of documenting an unscheduled visit.

² See important information in section 6.2.5 for guidance on Unscheduled Visits after wound closure.

³ "TV" = Treatment Visit

⁴ Study Ulcer Assessments include: 1) location 2) duration 3) size 4) exudate 5) infection 6) measurement of ulcer area

⁵ Collect pre- and post-debridement images

⁶ Collect pre-debridement image; if performing debridement, collect post-debridement image

⁷ Post-application image required if randomized to PriMatrix

⁸ Image of the closed wound area to be taken

⁹ Debride, if necessary

¹⁰ If randomized to the Standard of Care cohort

¹¹ Not required for dorsal wounds; required for plantar ulcers or lateral ulcers that would benefit from offloading

¹² If randomized to the Active Treatment and if necessary; see Section 5.17 for guidelines on applying PriMatrix

¹³ Optional application of PriMatrix. See Section 5.17 for guidelines on applying or re-applying PriMatrix

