6. SAMPLE SIZE DETERMINATION AND RATIONALE

This is a randomized study with two treatment groups. Assuming:

- 46% of DFUs receiving PriMatrix close by 12 weeks (84 days).
- 26% of DFUs receiving with Standard of Care close by 12 weeks (84 days).

Overall 2-sided Type I Error rate (alpha) of 0.05. Under the above assumptions, 102 subjects per treatment group will be required to meet the Type I error rate of 0.05 and 80% power; for a total

of 204 subjects for the study. As the treatment duration is short, the discontinuation rate is predicted to be around 15%. To accommodate the potential discontinuations, 240 subjects will be randomized (120 per treatment group) to this trial. The subjects will be randomized to the treatment groups in a 1:1 ratio.

A single interim analysis when 50% of subjects complete the trial, using group-sequential methods and Pocock alpha spending function, where the hypotheses will be tested at a two-sided alpha of 0.031 at the interim analysis and at a two-sided alpha of 0.028 at the final analysis.

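### The PEP dates leave 79 days, not the 84 days the SAP counts as 12 weeks, and the SAP specifies no CMH comparison of the primary endpoint in all randomized subjects

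*SAP*

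**What the plan says.** SAP 10.4 cites COVID-19 restrictions and lower loss to follow-up than planned for the decision to "terminate screening/enrollment prior to reaching the full enrollment of 240". It takes 21 May 2020 as the date for fixing the primary analysis set. Then "it was determined that subjects randomized by 3/3/2020 will be included in the PEP", and the justification is "All randomized subjects within the PEP will have enough time to go through the 12 weeks treatment phase by 5/21/2020".

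SAP 11.1.1 sets the timing: "The primary efficacy analysis will be conducted when all patients who were randomized on or before 03 March 2020 completes up to 12 weeks". The wait is for follow-up as well as treatment, and the section points back to 10.4 for the population. It adds that "207 patients will be included in the PEP".

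The SAP's own measure of 12 weeks is in section 6: "46% of DFUs receiving PriMatrix close by 12 weeks (84 days"). The schedule in SAP 5.2 puts TV13 at day 84 ± 3 and lists "Conf Visit 7±3d After Closure". SAP 11.1 requires closure to be confirmed one week later.

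Protocol 8.10.1 defines ITT as everyone randomized, and Protocol 8.12.1 runs the primary CMH test in that population. SAP 11.1 runs it in the PEP.

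**The concern.** There are two linked problems.

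- **Dates.** The reason given for pairing 3 March with 21 May appears not to fit the SAP's own length of treatment. SAP 11.1.1 refers back to 10.4, so a reader could take 21 May as the end of usable data. Late closures in the last-randomized subjects, or closures awaiting confirmation, could then count as failures.
- **Population.** The SAP narrows the primary population by randomization date and does not keep the protocol's comparison alongside it. The trial is open-label with an investigator-assessed endpoint, and SAP 10.4 does not say when the 3 March date was chosen. The all-randomized comparison is the simple check that the cut did not matter.

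**Working it through.** **1. Interval.** Inputs are 3 March and 21 May 2020 (SAP 10.4).

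28 days left in March + 30 in April + 21 in May = 79 days, or 80 if both ends are counted. The sentence needs 84.

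**2. Visit dates for a subject randomized on 3 March** (visit days from SAP 5.2):

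| Milestone | Day | Date | Days past 21 May |
|---|---|---|---|
| TV12, nominal | 77 | 19 May | fits |
| TV12, window end | 80 | 22 May | 1 |
| TV13, window start | 81 | 23 May | 2 |
| TV13, nominal | 84 | 26 May | 5 |
| Confirmation after TV13 closure, nominal (84 + 7) | 91 | 2 June | 12 |
| Same, both windows at their latest (87 + 10) | 97 | 8 June | 18 |

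Neither inclusive counting nor the visit window makes TV13 fit.

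**3. A possible source of the error.** The documents number weeks in two ways. Protocol 6.2.1 calls the day-7 visit Week 2, and footnote 14 of the SAP schedule ties Week 13 to TV13. On that numbering Week 12 is TV12, day 77. Protocol 8.6 instead treats Week 12 and TV13 as the same point, and SAP section 6 equates 12 weeks with 84 days. On the TV12 reading, nominal confirmation of a TV12 closure is 77 + 7 = day 84, or 26 May, still after 21 May.

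**4. Subjects affected.**
- 21 May − 84 days = 27 February, so those randomized 28 February to 3 March (5 days) had not reached day 84.
- 21 May − 91 days = 20 February, so those randomized 21 February to 3 March (12 days) had not reached day 91.

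Actual accrual is not given. I assume 5 to 15 a month; the upper value is the protocol's planned 30 sites × 0.5. With 30.44 days a month:
- Day 84: 5 × 5/30.44 = 0.8, to 15 × 5/30.44 = 2.5.
- Day 91: 5 × 12/30.44 = 2.0, to 15 × 12/30.44 = 5.9.

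**5. Analyses of the primary endpoint, side by side.**

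| Source | Population | Method |
|---|---|---|
| Protocol 8.12.1 | All randomized | CMH |
| SAP 11.1 | PEP | CMH |
| SAP 11 and 12.8 | Per protocol: no 3 March limit, major violators removed | Same as primary |
| SAP 13.1 (site 109) | PEP | Not specified |
| SAP 11.4 | SAP's ITT: randomized and treated (10.1) | Covariate analysis; no treatment contrast or test named |

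No SAP entry is a CMH test in all randomized subjects.

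**6. Subjects outside the PEP.** Enrollment stopped before 240, so at most 239 were randomized, and 239 − 207 = 32. The range is 0 to 32.

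**7. Minor: LOCF.** The SAP definition of complete closure requires confirmation, and SAP 11.5 makes subjects without complete closure failures. SAP 11.1 also applies LOCF to missing values in the primary analysis. It does not say whether LOCF may fill a missing confirmation visit.

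**The case against.** **The date error may have no consequence.** SAP 10.4 uses 21 May to decide who is in the set, and nothing calls it a data cut-off. SAP 11.1.1 waits for completion, and SAP version 1.0 is dated 3 August 2020, 62 days after day 91 for the last PEP subject. This stands: if data run through confirmation, no outcome changes. The sentence still has to be reconciled with 11.1.1.

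**Week 12 may mean TV12.** In Protocol 6.2.2 a subject still open at TV13 receives no further treatment application, so the last treatment visit would be day 77, which fits. This makes the ambiguity real. It does not rescue the sentence against the 84 days in SAP section 6.

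**The sentence covers the treatment phase only.** Both schedules place confirmation in follow-up. That is correct, so the shortfall against the sentence itself is 5 days, or 2 at the window edge. The day-91 figures matter because the endpoint needs confirmation.

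**The population gap may be narrow.** Randomization and first treatment are consecutive steps of one visit, so the SAP's ITT should be nearly everyone randomized. Its covariate analysis is meant to show robustness. The per-protocol CMH test includes later subjects without major violations. The cut applies to both arms and has a stated reason, and the number excluded may be zero. These points narrow the gap but do not close it: none supplies the protocol's comparison, and silence on timing is neither evidence for nor against an outcome-driven choice.

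**LOCF is a separate matter.** Fair; it is only a wording point.

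**Conclusion.** Both main points hold, and the SAP should be corrected. That 79 days falls short of 84 is calendar arithmetic. Its likely effect on results is small: about 1 to 2.5 subjects short of day 84 and 2 to 6 short of day 91, on the assumed accrual, and none with a changed outcome if data are used through confirmation as SAP 11.1.1 implies. The missing all-randomized CMH comparison is a direct departure from the protocol on which the SAP says it is based. Its importance depends on how many subjects were randomized after 3 March, which the documents bound only at 0 to 32. If the number is zero, the PEP is everyone randomized and one sentence saying so settles the point. The documents do not show that data were truncated at 21 May or that the cut was chosen with knowledge of outcomes.

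**What to change.** 1. **Dates.** Correct or delete the 21 May sentence in SAP 10.4. State in 10.4 and 11.1.1 that each PEP subject's outcome is used through TV13 and the confirmation visit, whatever the calendar date. State which visit Week 12 means; Protocol 8.6 and SAP section 6 point to TV13, day 84. If a date is kept with the 3 March cut, day 91 is 2 June 2020 and day 97 is 8 June 2020.
2. **Population.** Add the same CMH analysis in all randomized subjects, using the protocol's ITT definition, as a sensitivity analysis. Report by arm the number randomized after 3 March.
3. **Minor.** State in SAP 11.1 and 11.6 that LOCF does not apply to the binary primary endpoint, so that unconfirmed closure counts as failure.

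The cost is SAP wording and one extra table, produced at the final database lock that 11.1.1 already plans. The last randomization date is not given. If it was on or before 28 April 2020 (3 August 2020 − 97 days), every subject had passed day 97 by the date of SAP version 1.0. Subjects who discontinued without closure already count as failures under SAP 11.5.

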11. DESCRIPTION OF EFFICACY ENDPOINTS AND ANALYSES

The analyses of the primary efficacy endpoint will be performed using the PEP. The sensitivity analysis of the primary endpoint will be performed for the PP population. All secondary efficacy endpoints will be performed using the PEP. Safety analysis will be based on the safety population.

